1. SF-36

2. Quality of Life Enjoyment and Satisfaction Questionnaire (Q-LES-Q SF)

Demographics & History

- 1. History of Medical and Tick-borne Illness, Medical Utilization
- 2. Demographics+ Identifying Information Form
- 3. Physical History Form x 2 (completed by the MD)
- 4. Stressful Life Events Scale
- 5. NTSS6, TSS
- 6. Cumulative Illness Rating Scale (CIRS)

Sensory and Neuro testing (These procedures will not be conducted at NYSPI at present due to COVID-19)

- 1. Sensitivity to sound, light, vibration, pressure (in-person only)
- 2. Heart rate variability (in-person only)
- 3. Sudomotor small fiber function (Sudoscan) (in-person only)

Side-effect Monitoring

1. SAFTEE

Please attach copies, unless standard instruments are used

Off label and investigational use of drugs/devices

Choose from the following that will be applicable to your study ✓ Drug Select the number of drugs used in this study 1

Drug #1

Name of the drug Disulfiram Manufacturer and other information

Disulfiram is FDA approved to help individuals wishing to abstain from alcohol. There are several manufacturers of disulfiram.

Approval Status IND is approved IND# 142979 Who holds the IND/IND sponsor? IND is held by PI/CU Investigator [name], MD

Research Related Delay to Treatment

Will research procedures result in a delay to treatment? Yes

Maximum duration of delay to any treatment

We are asking patients not to start any new treatments during the course of this study and for 3 months prior. Therefore, the delay in starting any new treatment will be approximately 6.5 months.

Treatment is provided to all the participants. However, the participants who are randomized to the shorter dose regimen will receive 26 days of treatment compared to the participants who will get treatment for 54 days.

Maximum duration of delay to standard care or treatment of known efficacy

There is no treatment of known efficacy for patients with post-treatment Lyme disease.

Treatment to be provided at the end of the study

Patients will be offered the option of 3 months of symptom-based clinical treatment at the end of the study. The clinician visits at PI will be free. Patients will be given scripts of medication if needed, the cost of which will be covered by them or their insurance carrier.

Clinical Treatment Alternatives

Clinical treatment alternatives

The treatment of post-treatment Lyme disease symptoms is a matter of considerable uncertainty. Some health care providers offer repeated courses of antibiotics while other health care providers offer symptom-based therapies. Unfortunately too few studies have been conducted among patients with post-treatment Lyme disease to recommend specific treatments.

Risks/Discomforts/Inconveniences

Risks that could be encountered during the study period

Treatment with Disulfiram

1. Disulfiram-alcohol reaction. If patients consume alcohol or alcohol-containing products while on disulfiram, the patient may experience diaphoresis, palpitations, facial flushing, nausea, vertigo, hypotension, and tachycardia.

2. Disulfiram-related adverse effects.

a) Less serious side effects include headache, sleepiness, fatigue, and a metallic taste in the mouth.

b) More serious and rare side effects have been reported affect the following systems.i. Dermatologic. Rare reports exist of exfoliative dermatitis, rash, and pruritis.

ii. Liver. Rare reports exist of hepatitis, hepatotoxicity, and hepatic failure; there have been cases of fatal fulminant hepatic failure despite discontinuation of medication (1 case in 30,000 patients treated per year) (Stokes, Abdifadid Stat Pearls Publishing, October 2017).

iii. Psychiatric. Rare reports exist of psychosis, confusional states, mutisim, head banging, memory impairment, and stupor.

iv. Neurologic. Neuropathy occurs in 1 case per 10,000 patients treated with disulfiram per year. Cases of seizures and optic neuritis attributed to disulfiram have been reported.

v. Cardiac. Cases of heart failure and death have been reported in patients with significant coronary artery disease or heart failure.

vi. Genitourinary. Impotence has also been reported.

- 3. Disulfiram interaction with other medications.
- a). Disulfiram and cannabis increases the risk of psychosis.
- b) Disulfiram and metronidazole can lead to confusion or psychosis (hallucinations/delusions).

c). Interaction with compounds that use the P450 enzyme system for metabolism has been reported and is likely to occur. These include (but are not limited to): amitriptyline, imipramine, phenytoin, chlordiazepoxide, diazepam, omeprazole, and acetaminophen. Other drug-drug interactions have been reported as well.

4. Disulfiram may exacerbate certain conditions such as diabetes mellitus, hypothyroidism, seizure disorder, cerebral damage, cardiac, liver and renal disease.

Self -Report Questionnaires

Psychological distress at completing the self-report questionnaires.

Blood Draw

There is the risk of discomfort and a possible bruise at the site of the needle insertion. There is also a small risk of infection which can be treated if that occurs.

Sensory Testing (These procedures will not be conducted at NYSPI at present due to COVID-19.) Some participants might find the sensory testing mildly unpleasant. There is no significant risk to subjects associated with this kind of testing. The experimenter can stop the task at any time if the participant experiences discomfort and wants to discontinue the task.

Remote and hybrid participation during COVID-19 pandemic:

There are some risks associated with travel during the COVID-19 pandemic for participants completing study procedures remotely or via the hybrid protocol. The number of laboratory assessments and in-person assessments has been reduced to minimize risk. Nonetheless, for safety-related reasons, it will still be necessary for participants to attend some assessments in-person.

Describe procedures for minimizing risks

Treatment with Disulfiram

1. Disulfiram-alcohol reaction. Patients are required to be alcohol-free during this study and for at least 2 weeks prior to starting the study and for 6 weeks after receiving the last dose of study medication (I.e from weeks 8-14). The consent form will describe this reaction so that patients will be aware of the typical symptom profile should he/she inadvertently consume an alcohol-containing product; this will also be described in detail to the patient by the study clinician. Patients will also be advised to check labels of all consumed products to ensure there is no alcohol within the food preparation (e.g., sauces, vinegar, cough medication).

2. Patients will be monitored for side-effects of the medication during the clinic visits and weekly phone check-ups. The number of pills taken (either 2 or 1 or none) each day can be adjusted based on tolerability

and clinician's judgment. Intolerable side effects or clinically severe worsening that is sustained for 2 consecutive assessments will result in withdrawal from the study.

3. To reduce the risk of rare but serious adverse effects, patients will be excluded from enrollment in the study if there is:

- a. Liver: evidence or history of liver disease or insufficiency
- b. Psychiatric: a lifetime history of psychosis or of bipolar disorder or recent or current suicidality
- c. Substance use: alcohol or substance abuse disorder within the past 2 years
- d. Neurologic: a lifetime history of seizures or history of abnormal EEG
- e. Cardiac: a current or lifetime history of coronary artery disease or heart failure.

As additional precaution against liver injury, patients will be monitored closely during the study, including blood tests at intake and after weeks 2, 4, 6, and 10. If the clinician notices mild ALT or Alk Phos elevation (e.g., ALT >ULN but <2x ULN or ALK Phos >ULN <1.5x ULN), then the patient will remain at the same dose and repeat testing in 2 weeks (as long as TB <1.5 ULN). If the clinician notices moderate or severe LFT elevation (e.g., ALT > 2x ULN or AlkPhos > 1.5x ULN or Bili > 1.5x ULN), then the patient will discontinue disulfiram, be monitored closely, and referred to their internist for further liver monitoring. The clinician will also monitor the patient for signs of hepatitis, such as fatigue, weakness, anorexia, nausea, vomiting, jaundice, malaise, and dark urine.

Because disulfiram may exacerbate certain conditions, patients will be excluded from participation who have a diagnosis of diabetes mellitus, hypothyroidism, seizure disorder, cerebral damage, cardiac, liver or renal disease

4. Drug interactions:

a. Patients will be warned not to take metronidazole or paraldehyde; as the latter is not available in the United States, we anticipate this to be an unlikely risk.

b. Patients will be advised to review all new medications (prescribed or over the counter) with his/her research clinician to ensure lack of drug interactions.

Self- Report Questionnaires

Patients will be told that they can skip questions if they are too distressing to complete.

Blood Draw (These procedures will be minimally conducted as needed at NYSPI due to COVID-19.) Gloves will be used to reduce risk of infection and the skin is wiped with alcohol prior to the blood draw; if an infection occurs, it will be treated.

Sensory Testing (These procedures will not be conducted at NYSPI at present due to COVID-19.) Some participants might find the sensory testing mildly unpleasant. There is no significant risk to subjects associated with this kind of testing. The experimenter can stop the task at any time if the participant experiences discomfort and wants to discontinue the task.

Remote and hybrid participation during COVID-19 pandemic:

The number of laboratory assessments and in-person assessments has been reduced to minimize risk. However, for safety-related reasons, participants will be required to attend some assessments in-person. To

minimize risks associated with travel, the clinician obtaining consent will have a frank discussion regarding the risks of travel when attending the local physician's office, visits to NYSPI, and all Quest lab visits. Discussion points will include maintaining social distance, wearing masks in public spaces, exercising caution when traveling in public, and following public health guidelines. Participants will be informed about implemented procedures at NYSPI to minimize COVID-19 exposure risk such as personal protective equipment (masks and face shields), frequent disinfecting of equipment, and social distancing when possible. Prospective participants will also be advised that if they have any concerns regarding their safety, they will be able to reschedule appointments.

Methods to Protect Confidentiality

Describe methods to protect confidentiality

New techniques and technologies are developed each year that when applied to blood samples can help facilitate new discoveries and biomarkers; that is one of the goals of Precision Medicine research. To enable us to take advantage of emerging technologies, we would like to keep participant samples for at least 10 years or as long as they are deemed useful for research purposes. However, participants have the right to request that their samples be destroyed at any time.

All of the patient's medical records, laboratory reports, and research data will be stored in locked files and will be kept confidential to the extent permitted by law. Medical records, laboratory reports, research binders, and medical charts will be available only to research staff, local consulting physicians, and Federal, State and Institutional personnel as part of routine audits. There are legal advocacy organizations that have the authority under State law to access otherwise confidential subject records, but they cannot re-disclose this information without the patient's consent. Any research data transmitted or stored electronically will use a number assigned to the patient, not the patient's name. As a part of our remote protocol, local physicians will fax all assessment results and notes to the study clinicians via a HIPPA compliant fax. Quest diagnostics, who will perform local laboratory tests, have provided access to a HIPPA compliant secure EHR portal. Study clinicians will access participant laboratory results via that secure portal.

All the shared samples will be assigned a unique subject ID and no PHI will be shared with the collaborators. Samples will be shared after obtaining a Material Transfer Agreement (MTA).

Will the study be conducted under a certificate of confidentiality? No

Direct Benefits to Subjects

Direct Benefits to Subjects

There is no direct benefit to the participants expected from participation in this research study. It is hoped,

however, that the knowledge gained from this study may lead to a significant public health benefit as we hope it will help establish the safety and suggest efficacy of disulfiram as a medication to treat chronic symptoms of Lyme disease. While we hypothesize that patients will experience a reduction in symptom burden as a result of participation in this study, we are not certain this will be the case. Therefore, at this point, we cannot state that there will be direct benefits to the subjects.

Compensation and/or Reimbursement

Will compensation or reimbursement for expenses be offered to subjects?

Yes

Please describe and indicate total amount and schedule of payment(s).

Include justification for compensation amounts and indicate if there are bonus payments.

Participants who live outside the NYC metro area and choose to participate in-person will be reimbursed for reasonable travel expenses up to \$100 per visit. The amount is considered proportionate to the costs of rail travel for participants that live along the Northeast corridor and/or cover costs incurred for paid parking. For participants traveling from interstate, the reimbursement may be used to subsidize the cost of accommodation for each visit. Remote participants will not receive reimbursement. During the COVID-19 Pandemic, we will reimburse travel for participants within and outside the NYC metro area so that it may be more feasible for them to avoid public transportation. Hybrid participants will be reimbursed for reasonable travel expenses up to \$200 per visit.

References

References

Long TE. Repurposing thiram and disulfiram as antibacterial agents for multi-drug resistant Staphylococcus aureus infections. Antimicrobial agents and chemotherapy. 2017 Jul 3:AAC-00898.

Study Objectives	A study is a preliminary investigation regarding the relative benefit of 4 vs 8 weeks of treatment with disulfiram. With this initial study, the investigators will be able to evaluate the side effects, tolerability and initial signs of the effectiveness of disulfiram in reducing symptoms among the 24 patients assessed. The results of this study will guide the investigators regarding whether a larger definitive randomized trial should be conducted, and which treatment schedule is optimal.
Primary endpoint	Week 10 evaluation.
Study Design	A small 14-week randomized placebo-controlled pilot study enrolling 24 patients with persistent symptoms despite prior antibiotic treatment for Lyme disease (known as Post-treatment Lyme Disease Syndrome). Among the 24 disulfiram-treated patients, half will get 8 weeks of disulfiram and the other half will get a shorter duration of disulfiram for 4 weeks followed by 4 weeks of matching placebo. After week 8, patients will be off pills for 2 weeks for the primary week 10 evaluation and then for another 4 weeks for the week 14 follow-up evaluation. This will be a double-blinded study; neither physician nor patient will know which treatment group the patient is assigned to. For details see PSF.
General Study Population	See PSF respective section
Inclusion- Exclusion Criteria	See PSF respective section
Study Assessments	See PSF respective section
Sample size	24 as of 04/02/2019. The study was terminated in 2022 with a sample size of 11.
Randomization	This will be a double-blinded study; neither physician nor patient will know which treatment group the patient is assigned to. Randomization is performed at New York Psychiatric Institute pharmacy when medication is issued to an enrolled participant. Randomization is performed in blocked of 12. The study unblind will occur when the enrollment is completed, and all patients finish their follow-up assessments.
Primary aim#1	To assess the safety and side effect profile of disulfiram among patients with post treatment Lyme symptoms. This will be assessed by SAFTEE (systematically) as well as recording all unanticipated adverse events/serious adverse events.
Primary aim #2	To investigate whether treatment with disulfiram results in a meaningful reduction in fatigue and improvement in the quality of life among patients

	with Post- treatment Lyme Disease. Fatigue will be assessed by the Fatigue Severity Scale (FSS) and quality of life will be assessed with the Quality-of-
	Life Enjoyment and Satisfaction Questionnaire (Q-LES-Q).
Secondary	1. We will examine whether there is a difference in the proportion of
aims and	responders on the fatigue scale among the 2 different dosing regimens (54
Exploratory	days over 8 weeks vs. 26 days over 4 weeks followed by placebo). We will
goals:	assess both the percentage of responders and magnitude of the effect.
8	2. We will examine whether there is an improvement on the secondary
	outcome measures.
	3. We will examine the side effect profile and drop-out rate associated with
	different treatment schedules of disulfiram.
	4. We will examine whether there are other self-report measures that are
	more sensitive in documenting change over time than the FSS and the Q-
	LES-Q. These other measures, for example, include the PROMIS 29 v2.0
	profile questionnaire, the SF-36, and the General Symptom Questionnaire
	(GSQ-30).
	5. We will examine whether tests of sensory function, autonomic function,
	and cognitive function change with treatment.
	6. We will examine whether the urine antigen marker of Borrelia
	burgdorferi (as assessed by the Ceres Nanoscience Urine Nanotrap assay) is
	present at baseline and not present after treatment.
	7. We will collect biological samples for future precision medicine studies to
	be stored in our repository.
	8. We will collect fecal samples to be probed by investigators interested in
	studying microbiome changes in response to disulfiram.
	9. We will also monitor patients' activity via the data generated by Fitbit-
	change in response to treatment.
Timing of	Analysis will be performed after the study is unblinded.
Analysis	
Analysis	We conduct intent to treat analysis which covers all enrolled patients who
Population	received a study drug and who participated in at least one post-baseline
	assessment.
Missing Data	Missing data is treated as missing at random
Interim	There is no interim analysis for the protocol.
Analyses and	
Data	
Monitoring	
Analysis Analysis Population Missing Data Interim Analyses and Data	The rationale for the Fitbit is that our primary outcome is fatigue. People who are less fatigued may be engaging in more activity, such as doing more steps during the day. Moreover, activity monitoring using a device such as a Fitbit is being increasingly used in research studies as a measure of the change in response to treatment. Analysis will be performed after the study is unblinded. We conduct intent to treat analysis which covers all enrolled patients who received a study drug and who participated in at least one post-baseline assessment. Missing data is treated as missing at random

Primary aim#1 analysis	Tables on all mortality rate, SAE and AE will be generated. To estimate safety, number of adverse events in active and sham treatment groups by the end of 10-week period will be computed and reported.
Primary aim#2 analysis	To investigate whether treatment with disulfiram results in a meaningful reduction in fatigue and improvement in the quality of life, a change in scores between the baseline and week 10 will be computed. We will calculate a number of participants who's change in score reached a minimal clinically significant difference (MCID) for each of the measures. MCID for Fatigue Severity Scale (FSS) and MCID for Quality-of-Life Enjoyment and Satisfaction Questionnaire (Q-LES-Q) is 6.8. A Log Odds ratio for 8-week and 4-week group will be computed along with the 95% confidence interval for this ratio. The 95% confidence interval provides considerably more information than testing a specific null hypothesis: it provides a range of plausible values for differences in these primary outcomes between treatment groups which can be used to inform research in larger studies.

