Have all study staff with a significant role in the design or implementation of the human subject components of this study received required training in human research subject protections? Yes

Is the study covered by a certificate of confidentiality? No

Overall Progress

Approved sample size

24

Total number of participants enrolled to date

11

Number of participants who have completed the study to date

10

Have there been any significant deviations from the anticipated study recruitment, retention or completion estimates?

Yes

Describe actions taken or planned to address these problems.

The study enrollment was stopped in 2021 for the following reasons: a) the treatment drop-out rate in our study due to adverse events has been higher than expected; b) funding for this project is nearly complete; c) our pilot study has provided useful information about the relative safety of lower doses of disulfiram and the possibility of benefit with treatment; and d) based on the literature, disulfiram is a drug with uncommon but serious risk of toxicity.

Comments / additional information

Sample Demographics

Select the # of samples applicable

Specify population

Patients with Post-Treatment Lyme Disease Syndrome

Total number of participants enrolled from this population to date

11

Gender, Racial and Ethnic Breakdown

Sex: Female (6, 54.0%) Male (5, 46.0%) Racial Background: American Indian or Alaska Native (0, 0.0%) Asian (0, 0.0%) Native Hawaiian or Other Pacific Islander (0, 0.0%) Black or African American (1, 9.0%) White (10, 91.0%) More Than One Race (0, 0.0%) Other: (0, 0.0%) Ethnic Background: Hispanic or Latino (2, 18.0%) Not Hispanic or Latino (9, 82.0%)

Summary of Current Year's Enrollment and Drop-out

Number of participants who signed consent in the past year 0 Number of participants currently enrolled 0 Did the investigator withdraw participants from the study? No Did participants decide to discontinue study involvement? No

New York State Psychiatric Institute INSTITUTIONAL REVIEW BOARD

Procedures

To create the protocol summary form, first indicate if this research will include any of the following procedures

- Collection of Biological Specimens
- ✓ Internet-based Data Collection or Transmission
- ✓ Medication Trial
- ✓ Medication-Free Period or Treatment Washout
- ✓ Neuropsychological Evaluation
- ✓ Off-label Use of Drug or Device
- ✓ Psychiatric Assessment
- ✓ Use of Placebo or Sham Treatment

Population

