3. We will examine the side effect profile and drop-out rate associated with different treatment schedules of disulfiram.

4. We will examine whether there are other self-report measures that are more sensitive in documenting change over time than the FSS and the Q-LES-Q. These other measures, for example, include the PROMIS 29 v2.0 profile questionnaire, the SF-36, and the General Symptom Questionnaire (GSQ-30).

5. We will examine whether tests of sensory function, autonomic function, and cognitive function change with treatment.

6. We will examine whether the urine antigen marker of Borrelia burgdorferi (as assessed by the Ceres Nanoscience Urine Nanotrap assay) is present at baseline and not present after treatment.

7. We will collect biological samples for future precision medicine studies to be stored in our repository.

8. We will collect fecal samples to be probed by investigators interested in studying microbiome changes in response to disulfiram.

9. We will also monitor patients' activity via the data generated by Fitbit- The rationale for the Fitbit is that our primary outcome is fatigue. People who are less fatigued may be engaging in more activity, such as doing more steps during the day. Moreover, activity monitoring using a device such as a Fitbit is being increasingly used in research studies as a measure of the change in response to treatment.

REMOTE PARTICIPATION CONSIDERATIONS:

Due to the challenges imposed with remote data collection, we will not address research aims addressing sensory and autonomic function (aim 5), or collection of biological specimens for our repository (aim 7). Capacity to address these aims is dependent on final numbers of in-person vs. remote study participation. In light of the current COVID-19 pandemic, no in-person procedures will be conducted at NYSPI and we are unable to estimate future in-person enrollments at this time.

Description of Subject Population

Sample #1

Specify subject population

Patients with Post-Treatment Lyme Disease Syndrome

Number of completers required to accomplish study aims

20

Projected number of subjects who will be enrolled to obtain required number of completers

24

Age range of subject population

New York State Psychiatric Institute INSTITUTIONAL REVIEW BOARD

18-65

Gender, Racial and Ethnic Breakdown Based on prior studies of individuals with Lyme disease, we anticipate the following gender and racial/ethnic group representation:

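### The SAP records termination at 11 but keeps objectives written for 24 patients, and it names no method for zero cells in its between-schedule log odds ratio

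*Combined protocol and SAP*

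**What the plan says.** **Size.** In the protocol's Description of Subject Population, the entry for "Number of completers required to accomplish study aims" is 20, and the entry for "Projected number of subjects who will be enrolled to obtain required number of completers" is 24. Under Overall Progress, enrolment to date is 11 and the entry for "Number of participants who have completed the study to date" is 10. The SAP's Sample size row gives 24 as of April 2019 and then states: "The study was terminated in 2022 with a sample size of 11".

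**Objectives and design.** The Study Objectives row of the same SAP still says the study will evaluate "initial signs of the effectiveness of disulfiram in reducing symptoms among the 24 patients assessed", and that the results will guide the investigators on "whether a larger definitive randomized trial should be conducted, and which treatment schedule is optimal". The Study Design row still describes 24 patients, half on each duration.

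**Analysis.** The Primary aim#2 analysis row counts participants whose change from baseline to week 10 reaches the minimal clinically important difference. It then states: "A Log Odds ratio for 8-week and 4-week group will be computed along with the 95% confidence interval for this ratio". No interval method is named, and nothing is said about an arm with no responders or only responders. The Randomization row gives blocks of 12. The Timing of Analysis row places the analysis after unblinding.

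**Caveat.** The protocol's Rationale concedes that the sample, then planned at 24, is probably too small for significant differences between groups. The SAP does not repeat this.

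**The concern.** The SAP was revised after the trial stopped, but only in one row. Its objectives and design rows describe a trial about twice the size of the one that was run. It does not say that the protocol's own completer figure was missed, and it leaves the statement about schedule choice without the protocol's caveat.

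The reduced size also matters for the planned estimate. An unadjusted odds ratio and its usual interval need at least one responder and one non-responder in each arm. With 12 per arm a failure of that condition is uncommon at most rates; with five or six it is a real possibility. If it happens and no method has been named, someone must choose a continuity correction, a penalised estimate or an exact method after seeing the unblinded data. In tables this small, that choice can materially change the reported odds ratio.

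**Working it through.** **1. The plan's own size.** The documents give no alpha, power, effect size or dropout rate, so neither 20 nor 24 can be derived. The two figures are consistent with each other: 1 − 20/24 = 16.7% loss. Against them, 11/24 = 46% of planned enrolment and 10/20 = 50% of the stated completers.

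**2. Arm split (inferred).** Allocation is half and half, in blocks of 12. If each block is balanced, 11 allocations from one block give 6:5. The documents state neither the split nor the number randomised; they say 11 enrolled. A 5:5 split is shown as well, for 10 completers.

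**3. Responder rates (assumed).** No active-arm rate is given. The Rationale gives 20-30% as a placebo reference and treats 30% or fewer responders as a negative finding in an arm. Rates from 20% to 50% are used here. Equal rates of 70% and 80% give the same results as 30% and 20%, by symmetry.

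**4. Probability that the estimate is undefined.** For arms of n1 and n2 with responder rates p1 and p2:

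P = 1 − [1 − (1−p1)^n1 − p1^n1] × [1 − (1−p2)^n2 − p2^n2]

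Example, 6:5 with both arms at 30%:
- Arm of six: 0.7^6 + 0.3^6 = 0.1184.
- Arm of five: 0.7^5 + 0.3^5 = 0.1705.
- P = 1 − 0.8816 × 0.8295 = 0.269.

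| Rates | 6:5 | 5:5 | 12:12 |
|---|---|---|---|
| 50% and 50% | 9% | 12% | 0.1% |
| 50% and 30% | 17-20% | 22% | 1.4% |
| 30% and 30% | 27% | 31% | 3% |
| 20% and 20% | 50% | 55% | 13% |

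The 17-20% range depends on which arm has six. Each figure is for one outcome measure.

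**5. Count of tables at 6:5.** There are 7 × 6 = 42 possible responder tables. Those with both arms mixed number 5 × 4 = 20, so 22 leave the unadjusted log odds ratio undefined. The 42 tables are not equally likely; step 4 gives the probabilities.

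**6. Precision when it is defined.** SE = √(1/a + 1/b + 1/c + 1/d), where a to d are the four cell counts.
- Narrowest interval: 3/6 against 2/5. OR = (3/3)/(2/3) = 1.5; SE = √(1/3 + 1/3 + 1/2 + 1/3) = 1.22; e^(1.96 × 1.22) ≈ 11. The 95% Wald interval is 0.14 to 16.5.
- Most extreme table: 5/6 against 1/5. OR = (5/1)/(1/4) = 20; SE = √(1/5 + 1 + 1 + 1/4) = 1.565; z = ln 20/1.565 = 1.91, below 1.96.
- Listing all 20 defined tables finds none whose Wald interval excludes 1.

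**The case against.** **Already disclosed.** The SAP states the final size, and the progress report gives enrolment, completion and reasons for stopping. The 24-patient wording is design text carried over from the protocol. This stands in part: a careful reader is not misled about the number of patients. But it is current SAP text, and it conflicts with the row that was updated.

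**No schedule winner is claimed.** A reader might infer that the SAP commits to declaring the better schedule. The documents do not support that. The SAP calls the study preliminary and plans an interval, not a test. The protocol makes the choice of schedule conditional on one regimen showing more promise. The defect is narrower: the aim "and which treatment schedule is optimal" appears in the SAP without the protocol's caveat and without adjustment to 11.

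**The trial has not been shown to fail its aims.** It is tempting to conclude that with 10 completers the aims cannot be met. The figure of 20 is a form entry with no stated power or precision basis, and it is not tied to the schedule comparison, which the formal aims list as secondary. What can be said is that the stated figure was not reached.

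**Failure of the estimate is not the usual case.** A reader might take from the 22 of 42 tables that the log odds ratio will probably be undefined. At rates near 50% the chance is about one in ten; it reaches 27% or more when both arms are at about 30% or below, or 70% or above.

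**The method is unspecified, not wrong.** An exact or penalised interval would satisfy the SAP's wording, so the Wald figures show only what the default would give. The responder counts, and the continuous analysis promised under Assessment of Outcome, would survive a zero cell. This stands, and it confines the defect to the named between-arm estimate.

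**Denominators.** Ten completers is not necessarily the analysis set. The SAP includes anyone dosed with one post-baseline assessment, and the protocol seeks week 10 data from those who discontinue.

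**Conclusion.** The concern holds, as a failure to update the SAP together with an unspecified method. The SAP records 11 patients while its objectives and design rows describe 24. It does not say that the 20-completer figure was missed by half, and it keeps the schedule aim without the protocol's caveat. On an inferred split of about 6:5, the unadjusted log odds ratio is undefined with probability between 9% and 50% for assumed responder rates from 50% down to 20%, against 0.1-13% at the planned 12:12. Where it is defined, a Wald interval at that split can never exclude 1. At this size the comparison can describe the two schedules but cannot by itself identify the better one. The probabilities rest on balanced blocks, independent responses and rates that the documents do not supply; the mismatch in patient numbers needs no assumption.

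**What to change.** - Restate the SAP's Study Objectives and Study Design rows for 11 enrolled and 10 completed, with the number randomised and analysed in each arm.
- Say that the protocol's figure of 20 completers was not reached.
- State that the between-schedule comparison is descriptive estimation and cannot by itself identify the optimal schedule, repeating the protocol's caveat on size.
- Report responders over patients assessed in each arm, for each measure, with exact 95% confidence intervals.
- Name, before unblinding, an exact or Firth-penalised odds ratio that still gives an interval with a zero cell. An exact conditional interval may then be bounded on one side only; a Firth estimate with a penalised profile-likelihood interval stays finite. A risk difference with an exact or score interval may be added.
- If unblinding has already happened, which the documents do not say, label the method as chosen afterwards.

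The cost is SAP wording, a routine change of method and a less favourable stated conclusion. No new data are needed.
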